Do working alliance, patient outcome expectations and self-efficacy predict response to treatment for Achilles tendinopathy: protocol for a longitudinal cohort study (MAP II study)

Introduction

Pain related to a tendon, termed tendinopathy, can be traumatic or insidious in onset and short-lasting or persistent in nature (1). Tendinopathy is common musculoskeletal condition; the incidence of tendinopathy is higher than osteoarthritis, for example (2). Achilles tendinopathy (AT) affects both active and sedentary individuals and can be characterised by reduced activity tolerance to specific tasks that load the tendon (3). This results in decreased activity participation such as walking, running and working (4).

Current clinical guidelines recommend exercise as the first line treatment for people with Achilles tendinopathy (5). However, the rate and extent of improvement in pain and disability varies (6). This variation suggests we need to understand what factors predict change so we can enhance our care. Previously it was suggested that exercise worked by improving the strength or structure of the tendon, but it has been reported that pain and disability can change without corresponding changes in strength or structure (7). This suggests that other factors might be important predictors.

Recent literature suggests cognitive and contextual influences such as self-efficacy, working alliance and expectations may be important factors for predicting change in pain and disability in tendinopathy and need investigation (6,8). Based on this need, high-quality research is warranted. To inform the development of this research, two recent studies have been undertaken. Firstly, a feasibility study was completed. This study aimed to understand if it was feasible to collect data using a secure website to explore the association and predictive relationship of working alliance, outcome expectations and self-efficacy with pain and disability in the management of AT (9). The second study was a process evaluation to gain insight into the procedures undertaken in the feasibility study (10). Seven patients were interviewed to discover what worked (and did not) from their perspective during the study. Based on the results from the feasibility study and the information from the interviews with patients,

using this website is feasible, but we have made some changes before proposing this larger study. These changes include better promotion of the study, how verbal recruitment strategies could be improved, and how communication between clinicians and researchers could be made better. Based upon this knowledge this proposal aims to understand if working alliance, patient outcome expectations and self-efficacy predict response to treatment for AT.

Design

A multi-centre, prospective cohort study

Setting

Participants will be recruited from physiotherapy services across the UK. Seven sites have expressed interest, providing an expected referral rate of 1750 people with AT over a twelve-month period.

Recruitment

Patients diagnosed with AT by their treating physiotherapist will be introduced to the study through a verbal discussion and then provision of a card detailing the study's website (www.managing-achilles-pain.com). If the consultation is over telephone or via video-link, the physiotherapist will forward the study details via email. The website hosts password protected information (the participant information sheet, consent form and the clinical outcome measures and predictive factors). The participant can freely read the participant information sheet and consent details without time constraint, and decide to participate or not. The flow of a participant through the study is described in figure 1.

Diagnosis of AT will be based on criteria from expert consensus: local Achilles tendon pain reproduced with load-based activity and tenderness on palpation (5). Prior to commencing recruitment, physiotherapists will receive a training package. This training is important to maximise physiotherapists investment in the study, and help them answer any immediate questions from participants (10). Training will be delivered by [name] using online resources and face-to-face, if requested and safe to do so. The training will ensure physiotherapists are familiar with the background, aim and processes of the study, as well as criteria for inclusion. Hence,

recruitment to this proposed study and subsequent data collection will not be restricted by limitations imposed by COVID-19.

Inclusion and exclusion criteria

For participants to be included in the study they are required to:

- be a minimum of 18 years old
- have access to the internet
- have an available email address
- to have support in place to understand written English if it is required
- be diagnosed with AT by their treating physiotherapist
- be undertaking treatment prescribed by a physiotherapist.

Participants will be excluded from the study if they have:

- not provided informed consent
- been diagnosed with Achilles tendon tear/rupture
- received surgery to the affected Achilles tendon
- pain in the Achilles region with movements of the spine or neural tissue.

[figure not shown]

Figure 1. Participant flow diagram

Care Pathways

The effect of treatment is not under examination; the care pathway for recruited patients will not change.

Ethical approval

HRA approval will be sought, along with approval from the relevant Research and Development departments at each site before research commences.

Patient and Public involvement

To inform this proposal, two preparatory studies have been undertaken which sought patients' and physiotherapists' involvement (9,10). Firstly, a feasibility study was completed. This study aimed to understand if it was feasible to collect data using a secure website to explore the association and predictive relationship of working alliance, outcome expectations and self-efficacy with pain and disability in the management of AT (9). Prior to commencement of the study, two patients were involved in the design of the website, the layout of the questionnaire and all other patient-facing material such as the participant information sheet used in this study. The second study was a process evaluation to gain insight into the procedures undertaken in the feasibility study (10). Seven patients were interviewed to discover what worked (and did not), from their perspective during the study. Based on the results from the feasibility study and the information from the interviews with patients, using this website is feasible, but we have made some changes before proposing this larger study. These changes include better promotion of the study, how verbal recruitment strategies could be improved, and how communication between clinicians and researchers could be made better.

To inform the development of this application, a Patient and Public involvement Group has been convened. The group consists of two people with Achilles tendinopathy and two members of the general public. Members of the group have reviewed the application for clarity of expression and readability. This has resulted in changes to the plain English Summary with the addition of bullet points and headings.

The group will continue to work with us for the duration of the project. We have budgeted for two further meetings over the duration of the project, and using guidance from the NIHR INVOLVE document 'budgeting for involvement', included £50 per person per meeting. To reduce burden, minimise risk relating to COVID-19 and maximise inclusivity of these meetings, members of the group can attend

virtually. Further advice will be sought into developing advertising, the participant information, the training provided for the physiotherapists, the communication of the project's progress (such as a newsletter) and on conclusions from any reports.

Predictors

The potential predictive factors will be self-reported using the secure website (www.managing-achilles-pain.com). These factors have been purposefully selected from prior research (6,8–10):

- Working Alliance measured by the Working Alliance Inventory Short-Form (WAI-SF) (11)
- Outcome expectation measured by the Global Rating of Change (12)
- Self-efficacy measured by the Pain Self-Efficacy Questionnaire (PSEQ) (13) .

Clinical outcomes

Changes in the self-reported measures of pain and disability will also be recorded using the website. Recent research has questioned the usefulness of the disease specific measure of disability, the Victorian Institute of Sports Assessment - Achilles (VISA-A) to accurately inform change in a patient's clinical status (14). Consequently, the primary clinical outcome measure will be the Lower Extremity Functional Score (LEFS) (15). The LEFS is recommended in current clinical guidelines to assess disability (5). Changes in self-reported pain will be measured the Numerical Pain Rating Scale (NPRS) (16).

Sample Size

With the significance level set at 5%, and adjusting for multiple testing, a sample size of 129 would provide more than 80% power to detect a minimum effect size of 0.3. Allowing for a 20% attrition rate, 159 participants will be recruited. The R project for statistical computing package (pwr.r.test) was used to calculate this sample size:

```
> pwr.r.test (r=.3,sig.level=0.05/6, power=.8,alternative="two.sided")
```

approximate correlation power calculation (arctanh transformation)

n = 128.9428

```
r = 0.3
sig.level = 0.008333333
power = 0.8
alternative = two.sided
```

Data Collection

Data from the clinical outcome measures and predictive factors will be collected on three occasions; at baseline, six weeks later and finally at twelve weeks following completion of the baseline questionnaire. A participant's email and telephone number will be collected at baseline and used to invite them to take the follow up questionnaires. To maximise response rates, non-responders will be sent one email and one text message reminder at two weeks and four weeks after an anticipated response.

Data analysis

A multiple linear regression is fitted for the clinical outcomes difference (12 weeks minus baseline) of LEFS and NPRS. Independent variables of the multiple linear regression are the predictor variables WAI-SF, GRC and PSEQ. Three predictor variables and two clinical outcome measures result in six hypothesis tests which are adjusted for multiple testing by the Bonferroni method.

Backward selection as secondary analysis is applied to analyse if collinearities impact the influence of the three predictors. Possible centre effects are investigated by fitting an additive centre effect and interaction effects using an analysis of covariance model.

Dissemination

The findings from this research may influence decision making between a physiotherapist and a patient. As such, patients and physiotherapists will be the target audiences to reach.

Dissemination to patients and physiotherapists will take place once the study is complete. To ensure it is effective and wide-reaching, despite the potential of an ongoing pandemic, we will use the study website to host a blog and a summary

infographic (which will be made available to download) detailing the findings of the research. These will be written using Plain English guidelines ensuring it is accessible to patients. To supplement this, but with the aim of providing more 'research-rich' detail, an online lecture will be developed and will be through YouTube. The link to the website and YouTube channel will be emailed to all participants and physiotherapists taking part in the research, as well as promoted on social media platforms such as Twitter. These online strategies will incur no additional costs to the project.

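### The planned regressions can show that a questionnaire is associated with 12-week change, but not that it predicts change beyond age, sex, activity level and baseline score

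*Protocol*

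**What the plan says.** The Introduction describes a mixed population ("Achilles tendinopathy (AT) affects both active and sedentary individuals"), and the eligibility criteria admit any adult. On data, the Recruitment section says the website holds "the participant information sheet, consent form and the clinical outcome measures and predictive factors". The Data Collection section says "Data from the clinical outcome measures and predictive factors will be collected on three occasions" and adds that "email and telephone number will be collected at baseline", for follow-up invitations. The measures named are WAI-SF, GRC and PSEQ as predictors, with LEFS (primary) and NPRS as outcomes. Age appears only as an entry limit. Sex and activity level do not appear as data items.

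The Data analysis section states "A multiple linear regression is fitted for the clinical outcomes difference (12 weeks minus baseline) of LEFS and NPRS" and then "Independent variables of the multiple linear regression are the predictor variables WAI-SF, GRC and PSEQ". Backward selection is a secondary analysis of the same three predictors. The only other term is centre, additive and in interaction, in a separate analysis of covariance. Baseline LEFS and NPRS are collected but enter only through the difference.

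**The concern.** The Introduction wants to know which factors predict change so that care can be improved, and the Dissemination section expects the findings may influence decisions between physiotherapist and patient. For that use, the useful question is whether a questionnaire adds to what the physiotherapist already knows at the first visit.

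Usual activity level and age could plausibly be related both to confidence in acting despite pain (PSEQ) and to change in a lower-limb function score. If so, a PSEQ coefficient from a three-predictor model mixes PSEQ's own information with theirs, and the planned analysis cannot separate the two. The same holds for WAI-SF and GRC, and for the baseline value of the outcome, which often relates to change.

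The form of the model can be supplemented later in an analysis plan. The data items cannot: an analysis plan can adjust only for what was recorded.

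**Working it through.** **Inputs from the protocol.** Two-sided alpha 0.05/6 = 0.00833; design correlation 0.3; power 80%; 159 recruited with 20% attrition, so 159 × 0.8 = 127.2, about 127 completers.

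**The plan's own figure.** The `pwr.r.test` algorithm, re-coded, gives n = 128.943 against the stated 128.9428. The simple Fisher formula gives ((2.638 + 0.842)/arctanh 0.3)² + 3 = 129.4. The stated calculation is reproduced.

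**Inputs assumed.** The protocol gives no link between activity, age or sex and either PSEQ or change. Take one binary characteristic (active or sedentary) with p = 0.5 active. The groups differ by d within-group SDs on PSEQ and by the same d on LEFS change, and PSEQ has no link of its own with change. Vary d over 0.3, 0.5 and 0.8.

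**Induced correlation.** With equal differences on both variables,

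r = p(1−p)d² / [1 + p(1−p)d²].

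- d = 0.3: 0.0225/1.0225 = 0.022
- d = 0.5: 0.0625/1.0625 = 0.059
- d = 0.8: 0.16/1.16 = 0.138

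In this symmetric case the same figures are the share of change variance explained by the characteristic: 2.2%, 5.9% and 13.8%.

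**Chance that the PSEQ test is significant.** With m = arctanh(r) × √(127 − 3) and critical value 2.638, the chance is Φ(m − 2.638) + Φ(−m − 2.638).

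| d | r | m | Chance of significance |
|---|---|---|---|
| 0 | 0 | 0 | 0.83% |
| 0.3 | 0.022 | 0.245 | 1.0% |
| 0.5 | 0.059 | 0.656 | 2.4% |
| 0.8 | 0.138 | 1.546 | 13.7% |

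The middle case is 2.4/0.83 = 2.9 times nominal. The calculation is bivariate with one omitted characteristic. WAI-SF and GRC in the model could absorb part of the effect, and several omitted characteristics could add to it.

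**Cost of adjusting.** Age (1 df), sex (1), activity in three categories (2) and the baseline outcome (1) add 5 terms, making 8 with the three predictors. For one coefficient with partial r = 0.3, f² = 0.09/0.91 = 0.0989. Power from the noncentral F at n = 127 and alpha 0.05/6 is:

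- with noncentrality f² × n: 80.4% with 3 terms, 80.3% with 8;
- with the more cautious f² × (residual df + 2): 79.6% with 3 terms (123 residual df), 77.5% with 8 (118).

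The loss is therefore between about 0.1 and 2 percentage points for the same partial correlation, before any gain from the change variance that the covariates explain.

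**The case against.** The strongest reply is that the protocol asks a prediction question. Its title and aim ask whether three factors predict response to treatment, and it claims no effect independent of age or activity. A questionnaire score that tracks outcome only because active patients score differently still predicts outcome. This stands. A reader might infer that the percentages above are inflated false-positive rates and that a significant PSEQ result would be spurious. The documents do not support that: for the stated aim the association would be real. The figures bear only on the further claim of added value.

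Second, a reader might infer that no patient characteristics are collected and that they are lost for good. The protocol does not say so. Its description of the website and of contact details is not presented as a complete list, the participant flow figure is not shown, the baseline questionnaire is not in the document, and the age limit has to be checked somehow. What can be said is that the protocol does not name these items.

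Third, the Introduction's sentence about active and sedentary people is background on who gets the condition. It makes no prognostic claim, so nothing in the analysis contradicts it.

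Fourth, the size is assumed and small in the central case, and the sign is open. If active patients start with higher LEFS and have less room to improve, omission could hide a PSEQ association rather than create one. This also stands.

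Finally, a supplementary adjusted model is often left to an analysis plan. That is fair for the model, but not for the choice of what to record at baseline.

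**Conclusion.** The point holds as a limit on interpretation that is cheap to remove. The regressions are fixed to three questionnaires, and the protocol names no baseline patient characteristics. The study can therefore report association with 12-week change but cannot support a statement that a questionnaire predicts beyond what is routinely known at the first visit. That matters because the findings are meant to inform decisions. It is not an error in the planned test or its significance level.

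Under the assumed range of 0.3 to 0.8 SD the effect on a PSEQ test runs from negligible (1.0% against 0.83%) to noticeable (13.7%), with 2.4% in the middle. These figures rest on an even split, equal differences on both variables, one omitted characteristic and no PSEQ link of its own. They show scale only and do not estimate the bias in this cohort.

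**What to change.** 1. Name age, sex and usual activity level before onset (for example sedentary, recreationally active, sport) as baseline items on the web form. If the form already has them, naming them in the protocol is enough.
2. Keep the planned regressions. Beside each, pre-specify a second model that adds these three items and the baseline value of the outcome (LEFS or NPRS, already collected).
3. Limit any claim of prediction beyond routine characteristics to coefficients that remain significant at 0.05/6 in the adjusted model. Report both sets of estimates with confidence intervals, since a coefficient that loses significance has not been shown to add nothing.

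Cost: three short questions, one more model per outcome and about five degrees of freedom from about 127 completers. No extra participants or contacts are needed. The power of the planned models is untouched, and the adjusted models lose at most about 2 percentage points for the same partial correlation. The items should be settled before recruitment starts, because any not recorded at baseline would be hard to obtain reliably later.

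### Time already spent in treatment is neither limited, listed as collected nor adjusted for, so for late joiners the 12-week change is only the remaining part of the response the study aims to predict

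*Protocol*

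**What the plan says.** The protocol's Introduction states the aim: to understand whether "working alliance, patient outcome expectations and self-efficacy predict response to treatment for AT".

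Four sections decide which part of a patient's response is measured.

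- **Recruitment:** "Patients diagnosed with AT by their treating physiotherapist will be introduced to the study through a verbal discussion". The approach follows diagnosis but is not tied to a first appointment. The patient may read the study material "without time constraint, and decide to participate or not".
- **Inclusion and exclusion criteria:** the patient must "be undertaking treatment prescribed by a physiotherapist". Surgery to the affected tendon is the only earlier treatment that excludes; earlier or ongoing physiotherapy does not.
- **Data Collection:** questionnaires fall "at baseline, six weeks later and finally at twelve weeks following completion of the baseline questionnaire". The data named across the protocol are the three predictors, the two outcomes, and an email address and telephone number.
- **Data analysis:** the outcome is a change score: "A multiple linear regression is fitted for the clinical outcomes difference (12 weeks minus baseline) of LEFS and NPRS". The terms of that model are then named, and none of them concerns time in treatment: "Independent variables of the multiple linear regression are the predictor variables WAI-SF, GRC and PSEQ".

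No section limits, records or adjusts for the time between the start of treatment and the baseline questionnaire.

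**The concern.** Two patients can both satisfy the text, one completing the form on the day of the first appointment and the other several weeks into a course of physiotherapy. Each contributes a 12-week difference, and the differences are pooled as one outcome. For the second patient, part of the response came before baseline, so the difference measures only the rest.

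The predictors are affected too. Working alliance (WAI-SF), outcome expectation (GRC) and self-efficacy (PSEQ) can shift once a patient sees how treatment is going. In a late joiner they may partly record a response already obtained, which weakens the time order that a prediction study relies on.

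What is at stake is interpretation. If enough participants join late, a weak association could mean that the factor does not predict response, or that it was measured too late to show it. Without a start date the analysis cannot tell these apart.

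**Working it through.** **1. The protocol's own figure.** Inputs from Sample Size: r = 0.3, two-sided level 0.05/6 = 0.00833, power 0.80. The arctanh method with the t-based critical correlation gives n = 128.94, as printed, and power 0.800 at n = 129. The plain Fisher formula agrees: ((2.638 + 0.842)/atanh 0.3)² + 3 = (3.480/0.3095)² + 3 ≈ 129.4. The figure is sound, but it contains nothing about when treatment began.

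**2. Illustrative model.** None of these inputs is in the protocol.

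- Total gain A has mean 20 and SD 10; error SD is 5.
- Recovery is exponential with rate k = ln 2 / half-life, for half-lives of 4, 6 or 10 weeks.
- A patient who joins t weeks into treatment has an expected 12-week change of A·c·e^(−kt), where c = 1 − e^(−12k).
- The predictor correlates 0.30 with the change of a patient who joins at t = 0, and is itself unaffected by earlier response.
- A share p of participants join evenly over weeks 0–12; the rest join at t = 0.

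Write m₁ and m₂ for the means of e^(−kt) and e^(−2kt) over participants, and ρ for the correlation of the predictor with A. Then

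- r = ρ·10·c·m₁ / √V
- V = 500·c²·m₂ − 400·(c·m₁)² + 25

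**3. Worked case: half-life 6 weeks, p = 0.5.**

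- c = 1 − 0.25 = 0.75.
- Calibration at t = 0: V = 100 × 0.5625 + 25 = 81.25, so ρ = 0.30 × 9.01/7.5 = 0.361.
- m₁ = 0.5 + 0.5 × 0.75/1.386 = 0.771.
- m₂ = 0.5 + 0.5 × 0.9375/2.773 = 0.669.
- V ≈ 79.6, so r = 0.361 × 10 × 0.578/8.92 ≈ 0.23.
- Power at n = 129 and level 0.05/6 is about 51%.

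**4. Range.** The three values in each cell are for half-lives of 4, 6 and 10 weeks.

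| Share joining evenly over weeks 0–12 | Correlation | Power |
|---|---|---|
| none | 0.30 | 80% |
| 10% | 0.28, 0.28, 0.29 | 71–77% |
| 50% | 0.21, 0.23, 0.26 | 39–64% |
| 100% | 0.16, 0.20, 0.23 | 21–51% |

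If instead everyone joins within the first two weeks, power is about 73–77%.

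**5. What a covariate recovers.** Adding time in treatment as a linear term raises power in the worked case from about 51% to about 65%, and in the 10% row from 71–77% to about 77–78%. It removes the spread that entry time adds to the outcome. It cannot restore response that occurred before baseline.

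**6. Dependence on the model.** A harsher variant uses time constants of 4, 6 and 12 weeks (half-lives of about 2.8, 4.2 and 8.3 weeks). It keeps the residual SD unchanged while the predictable part of the change shrinks. If all join over weeks 0–12, it gives power of 6–34% instead of 21–51%.

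**The case against.** The best defence is the recruitment route. Numbers are counted from referrals, and patients hear of the study from the physiotherapist who diagnosed them, with a card or an email from the consultation. That reads most naturally as an approach at or near diagnosis, so most participants may enter early. This stands. It makes the low-exposure results the more plausible ones, but the text neither requires early entry nor records it.

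Several stronger readings are tempting and are not supported:

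- **That the 12-week change is not the response to treatment for the cohort as a whole.** This is true only of those who join some way into treatment. For patients who complete the form at the start, the change is close to the early response.
- **That the study will have 21–64% power.** Those figures need half or all participants to join evenly over twelve weeks, and nothing in the protocol suggests this.
- **That true predictors must be diluted.** The calculation shows attenuation because it assumes predictors untouched by earlier response. If they are touched, the direction of the bias is not established.
- **That the wording on time to decide is an open enrolment window.** It is a consent safeguard. It sets no upper limit, but it is not a timing rule.
- **That the data could certainly never be untangled.** The named data may not be a complete list, and the participant flow figure is not available to check for timing.

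Two further defences fail. The protocol says the effect of treatment is not being examined, but its title and aim still concern response to treatment. A statistical analysis plan could add a covariate, but it could not supply a date that was never collected.

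**Conclusion.** The omission is certain from the written text: time in treatment at baseline is not bounded, not listed as collected and not in the model, although the aim is to predict response to treatment. Its size is not certain, because the share of late joiners is unknown. With 10% late joiners the loss is modest, from 80% to about 71–77%. It becomes serious only if late entry is common (39–64% at half, 21–51% at all). These figures rest on the assumed recovery curve, gain and error SDs, on predictors unaffected by earlier response, and on the protocol's own simple-correlation calculation at n = 129. The change is worth making because it is cheap and must be made before data collection; no fault in the protocol's own sample-size arithmetic is implied here.

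**What to change.** 1. Add one item to the baseline form: the date of the first physiotherapy appointment for this episode of Achilles tendinopathy.
2. Enter time from that date to the baseline questionnaire as a covariate in both regressions, for the Lower Extremity Functional Scale (LEFS) and the Numerical Pain Rating Scale (NPRS).
3. Then do one of two things. Either set an enrolment window counted from that first appointment, or restate the aim as predicting subsequent 12-week change in patients under physiotherapy. The protocol offers no basis for a particular window length, so the investigators should choose and justify it. It must leave enough contact with the physiotherapist for working alliance to be rated, so some exposure before baseline is unavoidable.

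The cost is one form item and one model term. A window would also lose patients already well into treatment. That loss should be small in practice, since 159 of 1750 expected referrals are needed (159/1750 = 9.1%). No patient's care changes.

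### The change-score regressions leave out the collected baseline LEFS or NPRS score, so a predictor related to starting severity can seem to predict response; adding it is a cheap, minor improvement

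*Protocol*

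**What the plan says.** Under Data analysis the protocol fixes the outcome, "A multiple linear regression is fitted for the clinical outcomes difference (12 weeks minus baseline) of LEFS and NPRS", and then the covariates: "Independent variables of the multiple linear regression are the predictor variables WAI-SF, GRC and PSEQ". Three predictors and two outcomes give six tests with Bonferroni adjustment. The only further model terms concern sites: "Possible centre effects are investigated by fitting an additive centre effect and interaction effects using an analysis of covariance model". No sentence enters the baseline LEFS or NPRS score as a covariate, although Data Collection provides it: "Data from the clinical outcome measures and predictive factors will be collected on three occasions", the first being baseline.

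The purpose is worded in two ways in the Introduction. One sentence says "we need to understand what factors predict change so we can enhance our care"; the closing aim says that the proposal "aims to understand if working alliance, patient outcome expectations and self-efficacy predict response to treatment for AT". Clinical outcomes again speaks of change: "Changes in the self-reported measures of pain and disability will also be recorded using the website". Sample Size claims that "a sample size of 129 would provide more than 80% power to detect a minimum effect size of 0.3", using a simple correlation at a two-sided level of 0.05/6.

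**The concern.** Subtracting baseline does not remove its influence. With equal SDs at both visits and an imperfect correlation between them, patients who start worse tend to improve more, so the change score is correlated with the starting score. This is a cohort, and predictors and outcomes are self-reported by the same patients, so nothing in the design makes self-efficacy, expectation or alliance independent of starting pain and disability. A predictor that is merely a marker of baseline severity then acquires a coefficient in the planned model. A reader who takes the result to mean that the factor predicts response among patients who start at the same level would be misled.

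There is also a possible cost in precision. For a predictor unrelated to baseline, the planned model leaves in its residual some variation that an already collected score could explain.

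**Working it through.** **Inputs.** From the protocol: 129 completers, two-sided alpha 0.05/6 = 0.00833, effect size r = 0.3, three predictors. Assumed, because the protocol gives no values: correlation of baseline with 12-week score (r01) of 0.5, 0.6 and 0.7; equal SDs at both visits unless stated; predictor values taken at baseline; correlation of the tested predictor with the baseline score (rp) of 0 to 0.5.

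**The plan's own figure.** The arctanh calculation used in the protocol gives n = 128.94 and 80.0% power at 129. It reproduces.

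**Step 1: a predictor that adds nothing once baseline is known.** With both SDs set to 1, its coefficient in the planned model is -rp(1 - r01), and its correlation with change has size rp(1 - r01)/sqrt(2(1 - r01)). At r01 = 0.5 and rp = 0.3 this is 0.3 × 0.5/1 = 0.15. With a single predictor the protocol's own test would reject in 17% of studies; at r01 = 0.7 the correlation is 0.116 and the figure is 9%.

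The planned model has three predictors. It was simulated at n = 129 with 8000 replicates per cell, predictors intercorrelated at 0.3 (assumed), and the other two related to baseline only through the tested one. Rejection rates of the planned model, nominal 0.83%:

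| r01 | rp 0.2 | rp 0.3 | rp 0.4 |
|---|---|---|---|
| 0.5 | 5.3% | 14.0% | 29.2% |
| 0.6 | 4.5% | 11.2% | 21.6% |
| 0.7 | 3.1% | 7.7% | 15.3% |

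Repeat runs differ by about one percentage point at most, hence about 3-5%, 7-15% and 15-30%. With the baseline score added, rejection is 0.6-1.1%.

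**Step 2: the reverse case.** If the predictor is truly unrelated to raw change, the planned model keeps its level (0.6-1.0%) and it is the adjusted model that rejects:

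| r01 | rp 0.2 | rp 0.3 | rp 0.4 |
|---|---|---|---|
| 0.5 | 7.3% | 22.9% | 52.1% |
| 0.6 | 5.2% | 16.0% | 36.8% |
| 0.7 | 4.1% | 10.1% | 24.1% |

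The two models test different hypotheses whenever rp is not zero.

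**Step 3: precision when rp = 0.** Adjustment leaves a share (1 + r01)/2 of the variance of change: 0.75, 0.80, 0.85. The partial correlation is 0.3/sqrt(share) = 0.346, 0.335, 0.325, and power rises from 80.0% to 92.1%, 89.8%, 87.4%. This equals 129/share = 172, 161, 152 completers. In the three-predictor simulation, power goes from 71-72% to 87%, 84%, 80%; the lower starting point comes from the assumed intercorrelation, not from omitting baseline.

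**Step 4: sensitivity to the SDs.** If the 12-week SD is k times the baseline SD, the share is k²(1 - r01²)/(1 + k² - 2k·r01). For k = 1.2 it is 1.08/1.24 = 0.87 at r01 = 0.5 and 0.734/0.76 = 0.97 at r01 = 0.7, so power is 86% and 81%. For k = 0.8 it is 98% and 97%. The induced correlation in Step 1 also moves, to rp(1 - k·r01)/sqrt(1 + k² - 2k·r01). At rp = 0.4 and k = 1.2 it is 0.4 × 0.40/1.114 = 0.144 and 0.4 × 0.16/0.872 = 0.073, against 0.200 and 0.155 with equal SDs.

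**Step 5: precision when rp is not zero.** In the three-predictor setting with equal SDs, the variance of the tested coefficient, adjusted over planned, is 0.78-0.89 at rp 0.2, 0.83-0.94 at 0.3, 0.91-1.01 at 0.4 and 1.03-1.14 at 0.5. The gain is gone at about 0.4-0.5.

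**The case against.** The strongest reply is that the planned model is complete and valid. Outcome and covariates are stated, the six tests are tied to them, and the Introduction and Clinical outcomes both speak of change. For crude association with raw change the coefficients are right and the tests keep their level. All of this stands. A reader might infer that the primary analysis is invalid or its false-positive rate inflated; the documents do not support that, because the inflation in Step 1 exists only if the effect given baseline is the target, and the protocol nowhere says so. Nor is the plan silent on whether its coefficients are crude: a covariate list without the baseline score settles it.

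A second reply is that moving the tests to the adjusted model creates the mirror problem if raw change is meant. Step 2 shows that it does, at about 4-52%. The remedy must therefore keep both models in the report.

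A third is that the precision gain is overstated. That is fair: a gain of 7 to 12 percentage points might be read as a bounded range, but it requires equal SDs and a predictor unrelated to baseline. With a 12-week SD 1.2 times baseline it is 1 to 6 points.

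What remains is that the aim is worded as predicting response to treatment, in a non-randomised cohort, and the one collected variable that is tied to change by construction is left out of the model.

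**Conclusion.** The point holds as a cheap improvement of minor weight, not as an error. If the results are read as what a factor adds among patients with the same starting score, the planned model can credit a predictor with the effect of baseline severity: roughly 3-5%, 7-15% and 15-30% false rejections at predictor-baseline correlations of 0.2, 0.3 and 0.4. Adjustment also helps precision for predictors weakly related to baseline, with no assured gain otherwise. These figures rest on the assumed r01 of 0.5-0.7, equal SDs, predictor intercorrelation of 0.3 and baseline predictor values. The false rejections vanish if the predictors are unrelated to baseline, and are smaller if the 12-week SD exceeds the baseline SD as in Step 4.

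**What to change.** In Data analysis, add the matching baseline score (LEFS in the LEFS model, NPRS in the NPRS model) as a covariate, base the six Bonferroni tests on these models, state that the coefficients are conditional on baseline, and report the unadjusted change regressions alongside. If the sponsor confirms raw change as the target, say so, keep the planned models for the tests and report the baseline-adjusted models alongside.

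The cost is about two sentences and one degree of freedom per model; no new data and no change to the sample size. The downsides are a conditional rather than crude interpretation for predictors related to baseline, possible residual bias from measurement error in the baseline score, and no assured gain in precision.
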